PROTOCOL TITLE:

VERSION DATE:

PROTOCOL TITLE:

Association between a Pharmacogenetic Algorithm to Predict Blood Pressure Therapy with Blood Pressure Response to Anti-Hypertensive Therapy.

PRINCIPAL INVESTIGATOR or FACULTY ADVISOR:

[name]

Pharmacy

[contact]

[contact]

STUDENT INVESTIGATOR:

N/A

VERSION NUMBER/DATE:

1: 9.22.17

PROTOCOL TITLE:

VERSION DATE:

REVISION HISTORY

Revision #	Version Date	Summary of Changes	Consent Change?

PROTOCOL TITLE:

VERSION DATE:

Table of Contents

After completing your protocol, right click on the Table of Contents below and select “Update Field.” If prompted, select “Update entire table.” This will automatically update the protocol sections and page numbers for you. Do this also each time you modify your protocol after initial approval.

1.0	Objectives	6
2.0	Background	6
3.0	Study Endpoints/Events/Outcomes.....	9
4.0	Study Intervention(s)/Investigational Agent(s).....	9
5.0	Procedures Involved	10
6.0	Data and Specimen Banking.....	13
7.0	Sharing of Results with Participants.....	13
8.0	Study Duration	13
9.0	Study Population	13
10.0	Vulnerable Populations	14
11.0	Local Number of Participants	15
12.0	Local Recruitment Methods	15
13.0	Withdrawal of Participants.....	16
14.0	Risks to Participants.....	16
15.0	Potential Benefits to Participants	16
16.0	Data Management.....	16
17.0	Confidentiality	18
18.0	Provisions to Monitor the Data to Ensure the Safety of Participants	18
19.0	Provisions to Protect the Privacy Interests of Participants	18
20.0	Compensation for Research-Related Injury	19
21.0	Consent Process.....	19
22.0	Setting.....	19
23.0	Multi-Site Research.....	19
24.0	Resources Available	19
25.0	References.....	20

PROTOCOL TITLE:

VERSION DATE:

ABBREVIATIONS/DEFINITIONS

BP/Blood Pressure

PROTOCOL TITLE:

VERSION DATE:

STUDY SUMMARY

Study Title	Association between a Pharmacogenetic Algorithm to Predict Blood Pressure Therapy with Blood Pressure Response to Anti-Hypertensive Therapy.
Study Design	Retrospective Association Study
Primary Objective	To retrospectively assess the effectiveness of the use of a patient's genes to predict which hypertension therapy is successful: 
1. Level of blood pressure control (<140/<90)2. Change in blood pressure from baseline to control

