Secondary Objective(s)	
1. Number of medications needed to obtain control2. Time to control3. Number of office visits to control4. Side effects from hypertension therapy5. Hypertension associated adverse events during the course of treatment
Research Intervention(s)/Investigational Agents	Association between blood pressure control and genetic variants important in blood pressure regulation.
IND/IDE # (if applicable)	
Investigational Drug Services # (if applicable)	
Study Population	Hypertensive patients who have achieved BP control
Sample Size (number of participants)	Up to 2000
Study Duration for Individual Participants	Less than one day

PROTOCOL TITLE:

VERSION DATE:

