3.0 Study Endpoints/Events/Outcomes

1. Primary Endpoint/Event/Outcome:

To assess the effectiveness of the use of a patient’s genes to predict which hypertension therapy is successful, as measured by:

1. Level of blood pressure control (<140/<90)
2. Change in blood pressure from baseline to control

2. Secondary Endpoint(s)/Event(s)/Outcome(s):

Blood Pressure control with respect to:

1. Number of medications needed to obtain control
2. Time to control
3. Number of office visits to control
4. Side effects from hypertension therapy
5. Hypertension associated adverse events during the course of treatment

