5. N/A

5.0 Procedures Involved

1. Study Design: Retrospective analysis of association with DNA variants with pharmacotherapy used to achieve BP control.

General Flow of Activities:

1. Patients identified via UMN AHC-IE and sent recruitment letter, consent, survey and buccal swab kit via FRA's recruitment mailing process.
 - a. An E-mail, Letter, survey information, are included along with this submission.
2. Subject collects buccal swab:

Using the collection kit consisting of two buccal swabs and two uniquely barcoded tubes the investigator, patient, or designee will remove the first buccal brush and scrape the brush end across the inside of a Subject's right cheek repeatedly (for five seconds using moderate pressure). The investigator, patient, or designee will place the brush end over the open buffer vial and press the opposite end of the swab stick to release the brush into the buffer and then close the vial. The process will be repeated on the left cheek. Each of the right and left cheek vial numbers must be recorded on the clinical review form and accountability log as right (R), or left (L).

PROTOCOL TITLE:

VERSION DATE:

3. The patients return completed consent, buccal kit, to Geneticure for sorting.
4. The signed consent form is sent to the PI ([name]) and the buccal swab in lysis buffer is sent to the University of Arizona Genomics core facility for Genotyping.
 - All genotyping is performed in a blinded manner looking at 19 single nucleotide polymorphisms.
5. \$30 sent to participant at the time the Geneticure team receives the buccal swab, consent, etc. The Geneticure team will perform any follow-up needed for participants who do not receive their payment, additional questions. Clinical questions will be forwarded to [name] as the PI
6. Research team (Fairview pharmacy residents [name] and [name]) conducts chart review and abstracts data onto CRFs
7. CRFs sent to Geneticure

Specific Study procedures:

Screening

- Identify Potential Study Subjects through AHC. Refer to the Inclusion and Exclusion Criteria sections of this protocol for a complete list of eligibility criteria.
- Obtain Written Informed Consent either in-person or via mail. Each potential study participant must be given time to review the IRB-approved informed consent form, have his/her questions answered to their satisfaction and sign the form prior to any study procedures being performed. A subject will be given a copy of the informed consent form.

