16.0 Data Management

1. Data Analysis Plan:

The Investigator is responsible to ensure the accuracy, completeness, and timeliness of reported data.

PROTOCOL TITLE:

VERSION DATE:

All data will be compiled within the Fairview system on secure servers. De-identified final data may be sent to Geneticure using a secure, password-protected Excel spreadsheet on a server that is only accessible to IRB-approved personnel and is fully auditable. The database will be validated prior to use in the study. All required data will be recorded on CRFs or paper facsimiles. Data collected within the CRFs will be supported by source documents as appropriate and may be updated to reflect the latest observations on the subjects participating in the study. Corrections to the source documentation will be made in a manner that does not obscure the original entry and will be dated and initialed by the Investigator or assigned designee. It is important for data entry to occur in a timely manner, therefore, data collected on source documents should be transferred into CRFs as soon as possible following study visits.

All data will be coded for statistical analysis (i.e. drug classes will be coded numerically and genotypes will be coded numerically). Subject's raw genetic data will be entered into the Geneticure for Hypertension algorithm. All data will be analyzed with SPSS v.20. Normality of the data will be assessed using Levene's test prior to statistical analysis and any correction for non-normal data distribution will be used. Descriptive statistics will be computed (average time for blood pressure control, average number of visits to the clinician for blood pressure control, age, height, weight, BMI, etc.).

Data will be initially analysed following the collection of samples/data from up to 600 subjects. Statistical tests will be corrected for the number of tests run (preservation of alpha). Ordinary least squares regression via univariate modelling will be used to estimate the magnitude of linearity between drug class that yielded the best blood pressure control and genetic profile of the subject. Multiple regression analysis will be performed to determine the impact of confounding variables (height, weight, age, race) on blood pressure control. For all statistical analyses an alpha level of 0.05 will be used to determine statistical significance.

Missing Data

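### No planned model relates genotype or the algorithm's output to a primary blood pressure endpoint, and the one genetic model depends on arbitrary code numbers if drug class enters as a single score

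*Combined protocol and SAP*

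**What the plan says.** **Aim.** The title promises "Association between a Pharmacogenetic Algorithm to Predict Blood Pressure Therapy with Blood Pressure Response to Anti-Hypertensive Therapy". The Study Summary describes the intervention as "Association between blood pressure control and genetic variants important in blood pressure regulation". Section 3.0 asks whether a patient's genes predict which therapy succeeds, measured by two primary endpoints: control below 140/90, and "Change in blood pressure from baseline to control". The design sentence in section 5.0 is narrower: "Retrospective analysis of association with DNA variants with pharmacotherapy used to achieve BP control".

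**Analysis.** Section 16.0, Data Analysis Plan, states two inferential models.

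- Univariate OLS will "estimate the magnitude of linearity between drug class that yielded the best blood pressure control and genetic profile of the subject"; no other planned model is said to use the genetic data.
- The other model has BP as its outcome and is described in one sentence: "Multiple regression analysis will be performed to determine the impact of confounding variables (height, weight, age, race) on blood pressure control".

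On data handling, it says that "drug classes will be coded numerically and genotypes will be coded numerically" and that each subject's "raw genetic data will be entered into the Geneticure for Hypertension algorithm". It states no use of what the algorithm returns. It requires correction for the number of tests, sets alpha at 0.05, and names Levene's test as the check of normality.

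**Sizing.** The Power Analysis in the same section compares mean arterial pressure (MAP) between genotype groups within one drug class. For WNK-1 under diuretics the means are 97.6 and 100.8 mmHg, with pooled SD 12.

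**The concern.** The endpoints, the models and the sizing contrast do not meet. A report that follows section 16.0 to the letter would give an association between drug class and genotype, and a BP regression on body size, age and race. It would not say how BP control or change in BP differs by genotype, or by whether the patient's drug class agrees with the algorithm. If the missing term is left to be filled in at the 600-subject analysis, the predictor (single variants, a score, algorithm match) could be chosen after the data are seen.

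The second issue is conditional. Section 9.0 allows five drug classes, alone or in combination. They have no natural order, and the plan does not say whether class enters as one score or as a factor, or which side of the regression is the outcome. Nor does it say how the best class is assigned when control came on a combination.

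**Working it through.** **1. The plan's own sample size.** Inputs from the Power Analysis: difference 100.8 − 97.6 = 3.2, SD 12, alpha 0.05, power 0.80. Assuming a two-sided test, n per group = 2 × (1.960 + 0.842)² × 12² / 3.2² ≈ 221 (222 with the t distribution). The plan says 300, which gives about 90% power. That mismatch is a separate matter. What matters here is that the calculation concerns MAP by genotype among users of one class.

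**2. Endpoints and models side by side.**

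| Element | Outcome | Genetic predictor | Primary BP endpoint modelled by genotype or algorithm? |
|---|---|---|---|
| Univariate OLS | Best-control class or genetic profile (side not stated) | Genetic profile | No; BP only defines the class |
| Multiple regression | BP control | None named | No |
| Power Analysis contrast | MAP within a class | Genotype | Not a planned analysis; MAP is not a listed endpoint |
| Algorithm | None stated | Receives the genotypes | No; its output has no stated role |

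**3. Why a single class score depends on the codes.** Let class k have code c_k, and let b_k be the slope of its 0/1 indicator on genotype. The slope of the score is Σ c_k b_k, with Σ b_k = 0. Renumbering the classes changes this sum, and reversing the codes flips its sign. A factor test uses the b_k jointly and does not change.

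*One simulated data set.* Assumed: 600 patients on one class each, allele frequency 0.4, class shares 30/25/15/15/15%, and 6 percentage points moved from class 2 to class 1 per allele. Over all 120 numberings the slope ran from −0.35 to +0.35 and p from 0.0002 to 0.86; 54 numberings gave p < 0.05. As a factor, F = 3.98 and p = 0.003 under every numbering.

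*Repeated simulation.* Assumed: 4000 data sets, the same shares at genotype 0, and log-odds per allele of −0.25 for class 1 and +0.5 for class 4. OLS power ran from 5% to 98% over the numberings, median 50%; the order of the list in section 9.0 gave 82%, and class as a factor 96%. With no true association, rejection was 4–6%, so a code fixed in advance does not inflate type I error. The 96% assumes that all 600 patients have a single class. With 400, 300 or 200 such patients it falls to 85%, 69% or 51%.

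**4. Power of the missing BP test.** Assume 30% of 600 on diuretics: 180 patients, split 90 v 90 by genotype. The standard error is 12 × √(2/90) = 1.789, and 3.2/1.789 = 1.789.

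- Alpha 0.05: Φ(1.789 − 1.960) = 0.43.
- Alpha 0.05/18 (the 18 variants in section 4.0): Φ(1.789 − 2.991) = 0.11. The documents also give 17 and 19 variants; either count leaves 11%.

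**5. Selection on control.** The Study Summary and section 4.0 describe patients with achieved control. The criteria in section 9.0 do not list control and exclude only BP above 190 or 120. As an extreme case, cap MAP at 90 + (140 − 90)/3 = 106.7. Truncating N(97.6, 12) and N(100.8, 12) there gives means of 92.96 and 94.62, so the 3.2 mmHg difference shrinks to 1.66.

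**The case against.** **The genetic model is relevant.** Relating genetic profile to the class that gave best control does address the design sentence in section 5.0 and the opening of the primary endpoint in section 3.0. This stands. What it leaves unmodelled is the two measures by which section 3.0 says success will be judged.

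**The gap may be wording.** Covariates described as confounders, in the sentence right after the genetic model, presuppose an exposure, most naturally the genetic one. This also stands and lowers the severity. But no exposure is named, and several candidates fit.

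**Numeric codes may be only data entry.** Software stores categories as numbers, and the model could be run with class as a factor. Then the coding harm does not arise. The reference to linearity makes a single score a plausible reading, not an established one.

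**This is a pilot that changes no prescribing.** That is so, but the protocol still sets an alpha, a multiplicity correction and a sample size, so it plans tests.

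**The illustrations rest on invented inputs.** Class shares, allele frequency and effects are assumptions. The MAP cap is a loose proxy: 150/80 has MAP (150 + 2 × 80)/3 = 103.3, below the cap, yet is uncontrolled. A history of control does not bound the most recent reading. The cohort behind the MAP figures may itself have been selected, so the truncation may double-count. These figures show direction only.

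**Conclusion.** The point holds on the text. Section 16.0 specifies no model with a primary BP endpoint as outcome and genotype or algorithm output as predictor, and the contrast that sizes the study is not among the planned analyses. Dependence on the coding is real only if class is a single score. Naming Levene's test as a normality check is an error as written, though a minor one.

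Three stronger readings are tempting and are not supported:

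- That the investigators did not intend to relate genotype to BP. The mention of confounders suggests that they did.
- That the OLS analysis has 5–98% power in this trial. That range belongs to one reading of the coding and one set of assumed inputs.
- That the coding produces false positives. For a code fixed in advance it does not.

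Because part of the gap may be wording and the repair is cheap, this is an important clarification rather than a defect that invalidates the study. The 43% and 11% power figures assume 180 diuretic users split evenly by genotype.

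**What to change.** - **Drug class.** State that it is categorical. Use a 0/1 indicator for each class taken, which handles combinations. Keep multinomial regression as a secondary analysis in monotherapy patients, acknowledging the smaller n. Fix in advance how the best class is assigned.
- **BP as a continuous outcome.** Name the genetic term: a linear model of on-treatment BP (change in BP if baseline is collected) on genotype, class indicators, genotype-by-class terms and the listed confounders. This contains the contrast used for sizing. If the algorithm returns a recommended class, which the documents do not describe, add agreement with the patient's own class.
- **BP control.** Fit the same predictors in a logistic model for most recent BP below 140/90, and report it as descriptive only if nearly all subjects are controlled. Reconcile the Study Summary and section 4.0 with section 9.0 on whether control is required. State that selection on control and response-driven switching can shrink these associations.
- **Multiplicity.** Apply the plan's own correction to these tests and state the resulting power.
- **Assumption checks.** Use residual plots for normality and Levene's test for equality of variance.

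**Cost.** Plan wording, standard models and slightly more analysis work; the stated power will look less favourable. Section 5.0 already records the most recent BP. Whether baseline BP is collected cannot be checked, because the attachment listing the other data items is not available. The algorithm's output must be kept for each subject as an analysis variable.

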4.0 Study Intervention(s)/Investigational Agent(s)

1. Description: A multigene panel comprised of genes with known functionality in the heart, vasculature, and kidney, that are known to influence BP. This study will be performed as a retrospective study on patients within the Fairview Health System. Patients will be those who have been previously diagnosed with hypertension and have a history of blood pressure control (<140/<90 for two consecutive office measures. The study will involve collection of a buccal swab (can be done at the patient’s home, by the patient) and a clinical chart review of the patient’s hypertension and medication history. From the buccal swab we will assess 18 SNPs in 11 genes (2) SNPs in ADRB1, (2)

PROTOCOL TITLE:

VERSION DATE:

SNPs in ADRB2, (1) in SCNN1A, (1) in ADD1, (2) in SLC12A3, (3) in WNK1, (1) in ACE, (3) in AGT, and (1) each in AGTR1, CYP2D6*4 and REN) with known functionality in the liver, heart, vasculature, and kidney.

2. Drug/Device Handling: The device used for sample collection is a buccal swab kit that gently removes cells from the inside of the cheek. The Geneticure kit contains two buccal brushes and two tubes of lysis buffer. The patient swabs their left cheek and deposits the end of the swab in the lysis buffer, then does the same for the right cheek. This swab is placed (by the patient) in lysis buffer (a small tube) and shipped to the study site, if collected off site. The swab is then shipped to the University of Arizona Genomics core facility for DNA extraction, quantification, and assessment of the genes listed above. The study is retrospective in nature and the DNA assessment will not influence prescribing, i.e. no drugs will be changed based on this analysis for the patients. No identifying information will EVER accompany the kit to the genetic testing facility.
3. IND/IDE: In-vitro diagnostic device and exempt from IDE.
4. Biosafety: N/A

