- Review Inclusion/Exclusion Criteria. The investigator and/or designee will review all criteria to determine if the subject is eligible for enrolment. Eligibility of all subjects must personally be confirmed by the Investigator and will be documented on the CRF.

Enrollment

- Assign Identification Number to Eligible Subjects.

Chart Review

- Record demographics, antihypertensive medical history and most recent blood Pressure. Data will be documented in the source document and recorded on the patient demographic form, including but not limited to the following:
 - Age
 - Sex

PROTOCOL TITLE:

VERSION DATE:

- Height
- Weight
- Race
- Ethnicity

(additional data for collection is included in the attachment entitled "metrics")

Specimen Collection

- Collect Buccal Specimen.

Subject Numbering

Subjects meeting the criteria for enrollment (and their specimens) will be identified by unique numbers that will be assigned sequentially by order of enrollment. The pre-assigned investigational site number will be prefixed with GCE and the identification number and separated by a hyphen (e.g., GCE-001etc.). Throughout the descriptions within the protocol the A swab will be referring to the swab that has originated from the right cheek, while the B swab will be that that has originated from the left cheek. To further clarify. Subject GCE-001 will be given two barcoded tubes. These barcode numbers should be recorded for each patient. These will also be recorded as originating from the right cheek (A) or left cheek (B).

At no time should any study paperwork or specimens be marked with the subject's name or any other traceable identifier except for the informed consent form, which is signed by the subject and kept at the site. At no time should the original (signed) or a copy of this form be collected by the Sponsor or its representative.

2. Follow-Up: Data will be collected for up to one year.

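### As written, the plan gives no genetic estimate adjusted for race: genetics and the plan's own confounders are never placed in the same model

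*Combined protocol and SAP*

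**What the plan says.** Section 16.0 (Data Analysis Plan) of the combined protocol and SAP describes two regression analyses.

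- **The genetic model.** "Ordinary least squares regression via univariate modelling will be used to estimate the magnitude of linearity between drug class" and genetic profile. The class in question is the "drug class that yielded the best blood pressure control and genetic profile of the subject". No covariate is listed.
- **The covariate model.** "Multiple regression analysis will be performed to determine the impact of confounding variables (height, weight, age, race) on blood pressure control". No genotype, algorithm result or drug-class term is listed.

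Section 5.0 (Chart Review) has six demographics "recorded on the patient demographic form, including but not limited to the following": age, sex, height, weight, race and ethnicity. Section 5.0 describes the design as "Retrospective analysis of association with DNA variants with pharmacotherapy used to achieve BP control", and section 4.0 says "the DNA assessment will not influence prescribing". Section 3.0 makes the primary question whether a patient's genes predict which therapy succeeds, measured by level of control and change in blood pressure.

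**The concern.** This is a non-randomised comparison. Drug class was assigned neither by genotype nor at random. The plan recognises the consequence, since it names four confounders, but it puts them in a regression that contains no genetic term. A regression of blood pressure control on race describes how control varies with race. It does nothing to a genotype estimate obtained from a different model.

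Race matters most among the four. If genotype frequencies differ by race, and prescribing or blood pressure also differs by race, then a genotype that predicts nothing about drug response could still be associated with drug class or blood pressure. The study could report that as pharmacogenetic prediction.

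There is a second gap. Read literally, neither regression has blood pressure as outcome and genetics as predictor, although both primary endpoints are blood pressure measures.

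**Working it through.** **1. The two models side by side (section 16.0).**

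| | Genetic model | Multiple regression |
|---|---|---|
| Genetic term named | yes | no |
| Drug class named | yes | no |
| Blood pressure control as outcome | no (used only to define the best class) | yes |
| Age, race, height, weight | none listed | all four |
| Sex, ethnicity | not listed | not listed |

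Models with both a genetic term and a listed covariate: 0 of 2. Of the six demographics in section 5.0, 0 are in the genetic model, 4 are in the multiple regression and 2 are in neither.

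**2. Does another section join them?** Section 3.0 lists endpoints only. Section 5.0 gives the design and the data items. The Missing Data paragraph of section 16.0 does not mention models. The Power Analysis compares mean arterial pressure between genotype groups on a given therapy (for WNK-1 on diuretics, 100.8 − 97.6 = 3.2 mmHg, pooled SD 12) and mentions no covariate. Nothing joins the two models.

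**3. Size of the possible bias.** For a binary covariate, the bias in an unadjusted genotype difference is (difference in covariate prevalence between genotype groups) × (covariate effect on blood pressure). The documents give neither factor, so there is no estimate. To show the scale under purely assumed inputs:

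- 5 points × 3 mmHg = 0.15 mmHg, which is 0.15/3.2 ≈ 5% of the WNK-1 sizing difference.
- 30 points × 8 mmHg = 2.4 mmHg, which is 2.4/3.2 = 75% of it.

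The range shows only that the answer depends on quantities not yet known.

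**4. Precision cost of adjusting.** Inputs: N = 600 (section 11.0) and one genetic term. Covariate degrees of freedom are age 1 + height 1 + weight 1 + race 4 (five categories assumed) = 7, or 9 with sex 1 and ethnicity 1. The covariates are assumed to explain none of the outcome, the least favourable case for precision. With R² the share of genotype variation explained by the covariates (assumed):

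SE ratio ≈ √{[(N − 2)/(N − 2 − df)] / (1 − R²)}

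- df 7, R² 0: √(598/591) = 1.006, up 0.6%
- df 9, R² 0: √(598/589) = √1.0153 = 1.008, up 0.8%
- df 9, R² 0.02: √(1.0153/0.98) = 1.018, up 1.8%
- df 9, R² 0.05: √(1.0153/0.95) = 1.034, up 3.4%
- df 9, R² 0.10: √(1.0153/0.90) = 1.062, up 6.2%

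**5. Cost of missing covariates.** If a fraction m lack a covariate (assumed), the SE is multiplied by 1/√(1 − m). For m = 5%, 570 remain and the factor is 1.026; for 10%, 540 and 1.054; for 20%, 480 and 1.118.

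**The case against.** The best reply is that adjustment is plainly intended and only loosely written. Calling the four variables confounders makes little sense unless they confound the relation between genes and outcome. A univariate step followed by a multiple regression is also a familiar sequence, and univariate can mean one outcome rather than one predictor. This stands as a statement about likely intent. A reader might infer that the investigators chose to leave the genetic result unadjusted, and the documents do not support that. But the text does not state the joint model either, and leaving it unstated means exposure, outcome and covariates could be chosen after the data are seen.

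A reader might also infer that leaving out sex is a confounding error of the same weight. That is not supported. For autosomal variants, genotype is not expected to differ by sex in the source population, so confounding by sex would have to come mainly from selection, and nothing in the documents shows it. Sex is a matter of precision or effect modification.

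It can further be said that this is described as a pilot or feasibility proposal, that no treatment changes because of it, and that adjusting for demographics leaves the larger problem of non-random prescribing. All true. The pilot remark, however, explains the lack of preliminary data for the power calculation and does not make the plan's own confounders optional. The last point limits what the fix achieves; it is not a reason to leave race out.

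Finally, adding covariates to a model of genotype and blood pressure alone would average over mixed treatments and miss the study question. That is correct, and the fix below therefore includes drug class.

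**Conclusion.** The point holds as one of specification. Followed literally, section 16.0 produces a genetic association that is not adjusted for race or any other confounder the plan names. That association can partly reflect race if genotype frequency differs by race and drug class or blood pressure does too. Whether this happens here, and by how much, cannot be determined from the documents. The stronger statement, that the result will be biased, is not supported.

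The plan should be corrected before analysis. Confidence is moderate, because the intended analysis may already be the right one. The precision cost of about 0.8% to 6% rests on 600 subjects, one genetic term, five race categories and an assumed R² of 0 to 0.10.

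**What to change.** Rewrite the modelling paragraph of section 16.0 to do the following.

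- **Outcomes.** Name attained blood pressure and change in blood pressure. A controlled/uncontrolled outcome may vary little if the sample is, as the Study Summary says, "Hypertensive patients who have achieved BP control", although the eligibility list in section 9.0 contains no such requirement.
- **Exposure.** Put the genetic term and drug class in the same model, either as concordance between the algorithm's prediction and the drug used, or as genotype within drug class (or a genotype-by-class interaction). Say how combination therapy, which section 9.0 allows, is handled.
- **Covariates.** Include age, race, height and weight with the exposure. Ethnicity and sex can be added, sex mainly for precision.
- **Reporting.** Give the unadjusted result as supportive, and state how many subjects are lost to missing covariates.
- **Drug-class regression, if kept.** Adjust it for the same covariates. Ordinary least squares on a numerically coded nominal class is a separate problem that adjustment does not cure.

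The cost is one paragraph and no new demographic data. Precision falls as shown in the working. Within-class or interaction models will cost more, by an amount that cannot be given because the split across classes and combinations is not stated. Subjects with missing covariates drop out, and section 16.0 plans no sensitivity analysis for missing data. Confounding by indication and by comorbidity would remain and should be stated as a limitation.
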